6.8. Concomitant Therapy

All medications entered on the CRF will be coded centrally and manually to the World Health Organization (WHO) preferred trade name and WHO drug preferred term (which will still contain some trade names) according to the current WHO drug dictionary. These two terms will be provided in study data tabulation model (SDTM) datasets and form the basis of enabling anatomical therapeutic chemical (ATC) levels to be programmatically mapped from the WHO drug preferred term. Anatomical therapeutic chemical levels chosen will consider both the AE associated with the concomitant medication and intention for use (IFU), as listed on the CRFs. These will be confirmed with the study physician prior to summarizing the data.

Prior medications are medications that ended prior to the first dose of study medication. These medications are discussed in Section [6.6.3](#), Prior and Post Discontinuation Therapies.

Concomitant medications will be listed for all randomized patients. The WHO preferred term, start and end dates, and indication for which the medication was taken will be listed.

Concomitant medications will be summarized by treatment group for each appropriate ATC level for the drug and WHO preferred term within ATC level for the safety population. A unique count of patients for each ATC level will be provided and if a subject has multiple instances of the same WHO drug preferred term, the subject will be counted only once in the summary table.

Radiotherapy received on study will be listed separately. The listing will be similar to the prior and post discontinuation listings discussed in Section [6.6.3](#).

6.9. Efficacy Analyses

The following are definitions of the primary and secondary efficacy endpoints:

Primary Endpoint:

- **Overall Survival (OS) duration** is measured from the date of randomization to the date of death from any cause. For each patient who is not known to have died as of the data-

inclusion cut-off date for a particular analysis, OS will be censored for that analysis at the date of last contact prior to the data inclusion cutoff date (contacts considered in the determination of last contact date AE date, lesion assessment date, visit date, and last known alive date).

Secondary Endpoints:

- **Time to Progression (TTP) duration** is measured from the date of randomization to the first date of objective progression of disease based on Response Evaluation Criteria in Solid Tumors (RECIST) version 1.1 prior to the start of any post-discontinuation anti-cancer therapy. For each patient who is not known to have had a progression of disease as of the data-inclusion cut-off date, date of death, or date of initiating any post-discontinuation therapy, time to progression will be censored for that analysis at the date of the patient's last tumor assessment prior to that date.
- **Time to Progression rate at 3 months, 6 months, 9 months, 12 months** is defined as the proportion of patients not having objective progression (based on RECIST version 1.1) at 3, 6, 9, and 12 months respectively after the time from date of randomization estimated from the TTP distribution.
- **Progression-Free Survival (PFS) duration** is measured from the date of randomization to the date of first observation of objective progression (based on RECIST version 1.1) or death from any cause, prior to the start of any post-discontinuation anti-cancer therapy, whichever occurs first. For patients who are not known to have died or progressed as of the data-inclusion cut-off date or as of the date of post-discontinuation anti-cancer therapy, PFS time will be censored at the date of the last tumor assessment prior to that date.
- **Progression-Free Survival rate at 3 months, 6 months, 9 months, 12 months** is defined as the proportion of patients not having objective progression (based on RECIST version 1.1) or death at 3, 6, 9, 12 months respectively after the time from date of randomization estimated from the PFS distribution.
- **Overall Response Rate (ORR)** is defined as the proportion of patients who achieved a best overall response of either complete response (CR) or partial response (PR). The overall response rate for each treatment group will be estimated by dividing the total number of responders by the number of patients qualifying for the tumor response qualified population (Section 6.11). Response will be evaluated based on the RECIST version 1.1 and mRECIST criteria. No confirmation of response is required. Overall response rate will be calculated separately for each evaluation criteria.
- **Disease Control Rate (DCR)** is defined as the proportion of patients who achieved a best response of CR, PR or stable disease (SD). This rate will be estimated for each treatment group by dividing the total number of patients that had CR, PR or SD by the number of patients qualifying for the tumor response qualified population (Section 6.1.1). Best response of SD is defined as disease that does not meet the criteria for CR, PR, or progressive disease (PD) and has been evaluated at least one time, and at least 6 weeks after

baseline assessment. Patients without a valid response assessment at least 6 weeks after baseline assessment are assigned a best response of nonevaluable unless progression has already occurred. Response will be evaluated based on the RECIST version 1.1 and mRECIST criteria. Disease Control Rate will be calculated separately for each evaluation criteria.

All time-to-event endpoints will be analyzed using the Kaplan-Meier method. Covariates may also be included in these time-to-event models to account for variation in survival time. A Bayesian model will be used to estimate the hazard ratio of overall survival between the treatment arms.

Table JBAS.6.3. An Overview of the Efficacy Analyses

Efficacy Endpoint	Statistical Analysis	SAS Procedures
Primary analysis:		
Overall survival (OS)	A Bayesian OS model to estimate the hazard ratio (HR) of OS (under strong prior) and 90% predictive interval between LY2157299 plus sorafenib therapy and sorafenib plus placebo therapy	Non SAS - FACTS
Secondary analyses:		
Overall survival	The same Bayesian OS model in the primary analysis will be repeated using a weak prior.	Non SAS - FACTS
	The same Bayesian OS model in the primary analysis is used in secondary analysis to estimate the HR between LY2157299 monotherapy and sorafenib plus placebo therapy	Non SAS - FACTS
	Kaplan-Meier method will be used to estimate median survival time, OS rate at 6 and 12 months, and its 95% confidence interval (CI) for the treatment arms	LIFETEST
	Proportional hazard model will be used to estimate the hazard ratio of survival and 95% CI between treatment arms	PHREG
Time to Progression (TTP)	Proportional hazard model will be used to estimate the hazard ratio of survival and 95% CI between treatment arms, controlled for other factors. (Note: Use stepwise methods, slentry and slexit criteria)	PHREG
	Kaplan-Meier method will be used to estimate median TTP, TTP rates at 3, 6, 9, and 12 months, and its 95% CI for the treatment arms	LIFETEST
Progression-free survival (PFS)	Proportional hazard model will be used to estimate the hazard rate and HR of TTP and 95% CI of the 3 treatment arms and between the treatment arms	PHREG
	Kaplan-Meier method will be used to estimate median PFS, PFS rates at 3, 6, 9, and 12 months, and its 95% CI for the treatment arms	LIFETEST
Overall response rate (CR or PR) Disease control rate (CR, PR or SD)	The overall response rate will be estimated from dividing the total number of responders (CR or PR) by the number of patients qualifying for tumor response qualified population defined in Section 6.1.1. The disease control rate will be estimated from dividing the total number of patients with CR, PR or SD by the number of patients qualifying for tumor response qualified population defined in Section 6.1.1. The exact 95% CI for ORR and disease control rate will also be provided for each arm	REQ

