## 8. Investigational Plan

### 8.1. Summary of Study Design

[figure not shown]
Study H9H-MC-JBAS is a 3-arm, randomized, multicenter, global (Asia), Phase 2 study of LY2157299 plus sorafenib therapy or LY2157299 monotherapy compared to sorafenib plus LY2157299-matched placebo therapy in patients with relapsed or progressed HCC. Patients who receive sorafenib and investigators will be blinded to the LY2157299 or placebo assignment for those arms.

Approximately 120 patients will be randomly assigned in a 1:2:1 fashion to 1 of 3 treatment arms: LY2157299 monotherapy, LY2157299 plus sorafenib 400 mg BID, or sorafenib 400 mg BID plus LY2157299-matched placebo ([Figure JBAS.8.1](#)). The monotherapy dose will be 150 mg BID (300-mg daily dose) for 14 days, followed by 14 days with no study drug. The LY2157299 dose used in combination with sorafenib will be determined based on the results of the JBAK study – Part C (dose will either be 80 mg or 150 mg BID [160-mg or 300-mg daily dose]). LY2157299 and matched placebo will be given for 14 days followed by 14 days of rest; sorafenib will be given each day during the cycle. A cycle is defined as 28 days in duration (a minimum of 26 days and a maximum of 31 days). The treatment period for LY2157299 must be a minimum of 10 days and a maximum of 14 days.

Patients may receive treatment until they met at least one of the discontinuation criteria ([Section 7.3.1](#)).

This Phase 2 study will be considered complete after 100 deaths for OS analysis have occurred. Patients still on treatment at the time that the study is considered complete may enter the treatment extension period and continue with the study treatment (see [Section 8.1.1](#)).

End of study (trial) is the date of the last visit or last scheduled procedure shown in the Study Schedule ([Attachment 1](#)) for the last active patient in the study. Consult regional standard operating procedures for further information.

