**Table JBAS.10.1. Secondary Efficacy Endpoints**

Endpoint	Definition
TTP	The time from the date of study randomization to the date of first observation of objective progression. For patients who are not known to have progressed as of the data-inclusion cut-off date, TTP will be censored at the date of the last objective progression-free disease assessment
PFS (based on RECIST v1.1)	The time from the date of study randomization to the date of first observation of objective progression or death from any cause, whichever occurs first. For patients who are not known to have died or progressed as of the data-inclusion cut-off date, PFS time will be censored at the date of the objective progression-free disease assessment
ORR (based on RECIST v1.1)	The proportion of patients who achieved a best overall response of either complete or partial response defined by RECIST v1.1. The ORR for each treatment group will be estimated by dividing the total number of confirmed responders by the number of patients who received at least 1 dose of study treatment

Abbreviations: ORR = objective response rate; PFS = progression-free survival; RECIST = Response Evaluation Criteria in Solid Tumors; TPP = time-to-tumor progression; v = version.

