### **12.2.7. Secondary Efficacy Analyses**

In addition to the above primary Bayesian analyses for OS, OS curves for each treatment arm will also be analyzed using the Kaplan-Meier product-limit method (Kaplan and Meier 1958). Two-sided, 95% CIs for median OS will be computed by the Brookmeyer and Crowley method (Brookmeyer and Crowley 1982). OS rates at 6 and 12 months will also be estimated using Kaplan-Meier estimates on the OS curve for each treatment arm. Associated 2-sided 95% CIs will also be calculated. Pairwise HRs along with 95% CIs between the 3 arms may be estimated using proportional hazards (PH) models. Additional exploratory analyses using PH models to control for other factors may be performed. Details will be specified in the statistical analysis plan.

TTP and PFS curves and TTP/PFS rates will be summarized (at 3 months, 6 months, 9 months, 12 months) using Kaplan-Meier estimates of the median survival times (including 95% CIs). Pairwise HRs along with 95% CIs between the 3 arms will also be provided. Additional exploratory analyses using PH models to control for other factors may be performed.

ORR based on RECIST version 1.1 and mRECIST will be estimated by dividing the total number of responders (complete response [CR] or partial response [PR]) by the number of who received at 1 dose of study treatment and had measureable disease at baseline. Exact 95% CIs by the method of Clopper and Pearson (Clopper and Pearson 1934) for each treatment arm will be provided.

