**Evaluation of Best Overall Response**

The best overall response (OR) is the best response recorded from the start of the study treatment until the earliest of objective progression or start of new anticancer therapy, taking into account any requirement for confirmation. The patient's best OR assignment will depend on the findings of both target and nontarget disease and will also take into consideration the appearance of new lesions. The best OR will be calculated via an algorithm using the assessment responses provided by the investigator over the course of the trial.

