### Confirmatory Measurement/Duration of Response

#### *Confirmation*

The main goal of confirmation of objective response in clinical trials is to avoid overestimating the response rate observed. The confirmation of response is particularly important in *nonrandomized trials* where response (CR/PR) is the primary end point. In this setting, to be assigned a status of PR/CR, changes in tumor measurements must be confirmed by repeat assessments that should be performed no less than 4 weeks after the criteria for response are first met. To confirm a response of CR, a full assessment of all target and nontarget lesions that were present at baseline must occur, including those measured by bone scan. To confirm a PR or SD, a full assessment of target lesions that were present at baseline must occur; assessment of nontargets is not required.

However, in *randomized trial* (Phase 2 or 3) or studies where SD or progression is the primary endpoint, confirmation of response is not required. But elimination of the requirement may increase the importance of central review to protect against bias, in particular of studies which are not blinded.

In the case of SD, follow-up measurements must have met the SD criteria at least once after start of treatment at a minimum interval not less than 6 weeks measured from the first dose.

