6.1.1. Analysis Populations

The following populations used for analysis are defined in [Table JBAS.6.2](#) below.

Table JBAS.6.2. Populations used for Analysis

Population	Definitions or Rule
Randomized	Patients who have been randomized to study treatment. Patients in this set will be grouped according to their allocated treatment. All subject characteristics and efficacy analyses (except tumor response) will be conducted on this population.
Per-protocol	Patients who have been randomized to study treatment and did not have any major protocol deviations. Patients in this set will be grouped according to their allocated treatment. Efficacy analyses might be conducted on this population in addition to the randomized population.
Tumor response qualified	Patients who have been randomized to study treatment, received at least 1 dose of study treatment (LY2157299, LY2157299-matched placebo, or sorafenib), had measurable disease at baseline and had at least one baseline and one study treatment period tumor assessment. Tumor response analyses (Section 6.9.2.2) will be conducted on this population. Patients in this set will be grouped according to their allocated treatment, and then the analysis will be repeated using the actual treatment assignment.
Safety	Patients who have been randomized to study treatment and have received at least 1 dose of study treatment (LY2157299, LY2157299-matched placebo, or sorafenib). Patients will be grouped according to actual treatment received in Cycle 1. Safety analyses and efficacy analyses as specified in Section 6.9.2.1 will be performed on this population.

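### ORR has conflicting definitions: the documents disagree on confirmation, and one of three denominators drops patients with no on-treatment tumor assessment

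*SAP*

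**What the plan says.** **Numerator.** Protocol Table JBAS.10.1, in the row for ORR by RECIST v1.1, estimates the rate by "dividing the total number of confirmed responders by the number of patients who received at least 1 dose of study treatment". Protocol 12.2.7, the section on the analysis, does not mention confirmation: "ORR based on RECIST version 1.1 and mRECIST will be estimated by dividing the total number of responders" (CR or PR). Protocol Attachment 9 derives best overall response "taking into account any requirement for confirmation" and, under Confirmation, says: "However, in *randomized trial* (Phase 2 or 3) or studies where SD or progression is the primary endpoint, confirmation of response is not required". SAP 6.9 says: "No confirmation of response is required".

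**Denominator.**
- Table JBAS.10.1 uses all dosed patients.
- Protocol 12.2.1 and 12.2.7 use dosed patients with measurable disease at baseline. SAP 6.9.2.2 gives the same definition in its ORR paragraph.
- SAP 6.9 and SAP Table JBAS.6.3 use the tumor response qualified population. SAP 6.1.1 defines this as randomized, dosed patients who "had measurable disease at baseline and had at least one baseline and one study treatment period tumor assessment".

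The closing sentence of SAP 6.9.2.2 assigns all analyses in that section to the third population, so the section contradicts its own ORR paragraph. The ORR definition in SAP 6.9 also points to Section 6.11, which covers pharmacokinetics, where 6.1.1 is evidently meant.

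**The concern.** ORR is a named secondary measure, estimated for each arm. As the text stands, two analysts could follow the documents faithfully and report different rates from the same data.

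The two parts of the conflict differ in kind. Confirmed and unconfirmed response are two legitimate definitions, and the reader needs to know which one is reported. The third denominator is a selection on what happens after randomization. A patient enters it only by staying alive and on treatment long enough to be assessed. Those left out have no on-treatment response, so removing them can only raise the rate or leave it unchanged. The rise depends on each arm's early losses, so it need not be the same in every arm.

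**Working it through.** The documents give no assumed ORR, no target ORR and no confirmation rate, so there is no stated figure to reproduce. What can be derived is the direction of each effect and, under stated assumptions, its size.

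**1. Confirmation: direction and unit of change**

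Confirmed responders are a subset of all responders. On one denominator, therefore, unconfirmed ORR ≥ confirmed ORR, with equality if every response is confirmed.

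Planned arms are 30 / 60 / 30 (Protocol 12.1). Each unconfirmed responder changes the rate by:
- n = 30: 1/30 = 3.3 percentage points
- n = 60: 1/60 = 1.7 percentage points

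Illustration for the 60-patient arm, assuming 6 responders of any kind, with exact 95% intervals:

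| Responses confirmed | ORR | 95% CI |
|---|---|---|
| 6 of 6 | 6/60 = 10.0% | 3.8 to 20.5 |
| 4 of 6 | 4/60 = 6.7% | 1.8 to 16.2 |
| 3 of 6 | 3/60 = 5.0% | 1.0 to 13.9 |

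The share confirmed is an assumption, so the total effect cannot be derived from the documents.

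**2. Denominator: deaths before the first scan**

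Inputs:
- First scheduled on-study scan: Cycle 2 Day 14 (Protocol Attachment 1). With 28-day cycles, 28 + 14 = 42 days, or 6 weeks.
- Control hazard: 0.0216 per week, exponential (Protocol 12.1 and SAP 5.2).
- Combination versus control HR: 0.667 (same sections).

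Assumptions: dosing starts at randomization; no qualifying assessment comes before the first scan; only deaths are counted.

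Share dying before 6 weeks = 1 − exp(−hazard × 6):
- Control: 1 − exp(−0.0216 × 6) = 1 − exp(−0.1296) = 12.2%, or 0.122 × 30 ≈ 3.6 patients
- Combination: 1 − exp(−0.0216 × 0.667 × 6) = 1 − exp(−0.0864) = 8.3%, or 0.083 × 60 ≈ 5.0 patients

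Take an illustrative ORR of 10% among all dosed patients in both arms. The responders stay in the numerator and the early deaths leave the denominator:
- Control: 10% / (1 − 0.122) = 11.4%
- Combination: 10% / (1 − 0.083) = 10.9%

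Two equal rates now appear about 0.5 points apart. Under the plan's own survival assumptions, the larger increase goes to the arm with more early deaths.

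**3. Denominator: a wider range**

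Patients who stop treatment before an assessment are also dropped, and the documents give no rate for this. For any share lost, 6 responders among 60 give:
- none lost: 6/60 = 10.0%
- 5% lost: 6/57 = 10.5%
- 10% lost: 6/54 = 11.1%
- 20% lost: 6/48 = 12.5%

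**4. The other two denominators**

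Inclusion criterion 3 requires measurable disease. All dosed patients and dosed patients with measurable disease should therefore differ only by patients enrolled in error. The difference that matters is between these two and the third.

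**The case against.** On confirmation, the strongest reply is that the SAP follows the protocol's own rule. Attachment 9 waives confirmation in a randomized Phase 2 trial, and Protocol 8.1 states: "Study H9H-MC-JBAS is a 3-arm, randomized, multicenter, global (Asia), Phase 2 study". Section 12.2.7 adds no confirmation requirement. The word confirmed appears only in the table row for RECIST v1.1, and the mRECIST attachment cannot be read in the public version. This reply stands, and it rules out three stronger readings that a reader might infer:

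- *That the SAP's ORR is not the protocol's endpoint.* The protocol contradicts itself. The SAP departs from Table JBAS.10.1 but agrees with Attachment 9 and is compatible with Section 12.2.7.
- *That unconfirmed ORR is biased in itself.* It is a different definition, applied alike in every arm. It is higher only relative to a confirmed rate.
- *That the SAP revision history shows an undeclared change of endpoint.* That history lists main changes from Version 1 to Version 2. Version 1 is not available, and nothing shows that it required confirmation.

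Attachment 9 does warn that "elimination of the requirement may increase the importance of central review to protect against bias", especially in studies that are not blinded, and the monotherapy arm is open label. But Protocol 10.1.1 plans central review of all radiographic examinations for the final report, and SAP 6.9.2.2 repeats the investigator summaries on central reads, although only when those data are available. The two arms of the primary comparison are blinded to LY2157299 or placebo. This is not a separate defect.

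On the denominator, it can be said that ORR carries no test, power or decision rule, and that the shift is small beside the confidence intervals. Both are true and limit the importance of the point. The SAP also does not say whether the physical tumor examination in the Study Schedule, which comes sooner than the first scan, would qualify. If it did, fewer patients would be lost. None of this reconciles SAP 6.1.1 and 6.9 with Protocol 12.2.7 or with the ORR paragraph of SAP 6.9.2.2.

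**Conclusion.** The ORR definition is wrong as written and needs correction. The conflict on confirmation lies within the protocol: Table JBAS.10.1 stands against Attachment 9, with Section 12.2.7 silent, and the SAP settles it without comment. Its size is 3.3 or 1.7 points per unconfirmed responder; the total is unknown.

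The denominator has three versions, two of them within SAP 6.9.2.2. The version that needs an on-treatment assessment removes non-responders after randomization. Counting deaths alone, this is about 12% of control and 8% of combination patients, which moves an illustrative 10% ORR to about 11.4% and 10.9%. These figures rest on constant hazards at the planning values, the planned HR of 0.667, dosing at randomization and no qualifying assessment before about 6 weeks. Patients who stop treatment early would add to the shift. Fewer early deaths, or a sooner qualifying assessment, would reduce it.

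The primary OS analysis is not affected.

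**What to change.** - In SAP 6.1.1, 6.9 (with Table JBAS.6.3) and 6.9.2.2, use all dosed patients with measurable disease at baseline as the ORR denominator. Count patients without an on-treatment assessment as non-responders. Correct the cross-reference from 6.11 to 6.1.1.
- Reconcile Protocol Table JBAS.10.1 with Protocol 12.2.7, Attachment 9 and SAP 6.9 on confirmation, and record the choice and the reason for it.
- Report confirmed and unconfirmed RECIST v1.1 ORR side by side. Scans every 6 weeks (± 3 days) exceed the 4-week minimum interval for confirmation in Attachment 9, so no new data are needed. A response first seen at a patient's last scan has no follow-up scan and counts as unconfirmed; the table should say so.

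The cost is one extra derivation and table, and a slightly lower ORR.
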